Trial: **Caring Light for Family Caregivers**

ClinicalTrials.gov ID: **NCT04517877**

Date: **05/08/2022 (updated)**

Investigator: **[name]**

Research Site:

Photozig, Inc.
[name]
[name]
[name]

Project Summary

Every 66 seconds, someone in US develops Alzheimer's Disease, a progressive irreversible neurodegenerative disease, causing distress not only to dementia patients, but also to caregivers (15+ million), who are the hidden patients with high incidence of stress (60%) and depression (30%+).

Due to this significant problem, effective, low-cost, and accessible interventions are needed to help dementia caregivers to deal with the caring demands, heavy emotional toll, life changes, and overwhelming experiences.

A promising delivery mechanism is the smartphone, because: a) smartphone adoption is very high; and b) a large number of Americans nationwide have access to mobile broadband.

Therefore, we propose a unique intervention based on the Coping with Caregiving (CWC) curriculum, mindfulness, self-paced approach, and mobile app delivery, which has not been created before, called Caring Light App (CLA) to enhance caregiver coping skills, reduce stress, and alleviate depression.

Our project will have a high impact because: 1) the blending of CWC and mindfulness is expected to be very effective, based on our preliminary studies and other research results; 2) the proposed program is low-cost; and 3) CLA intervention will be accessible to a large group of caregivers as a mobile app, allowing its broad dissemination to innumerable families struggling with Alzheimer's and related dementia.

By integrating mindfulness practice with the CWC curriculum in a new mobile app, we will create a novel program for caregivers, blending training (coping skills, techniques to deal with dementia, practical tips on difficult behaviors, etc.) with stress reducing strategies (e.g. guided meditation, gentle stretches, and other mindfulness exercises), which is expected to be well accepted and easy to use by caregivers.

Protocol

Overview:

1. Recruit subjects: caregivers of individuals with Alzheimer's Disease or other dementia will be recruited.
2. Randomize subjects: participants will be assigned to the study group or the control group.
3. Collect pre-data: Before intervention, we will collect pre-data to establish the baseline status of participants.
4. Deploy treatments: For both study and control groups, we will send instructions and materials.
5. Collect post-data: We will collect post-treatment data after 3 months.

Research Participants: 150 dementia family caregivers (planned enrollment) will be recruited:

Inclusion Criteria:

- Care for an individual with Alzheimer's Disease or other dementia.
- Own a smartphone or tablet and have Internet access.
- Minimum age of 18 years old.
- Spend at least 8 hours/week caring for a person with dementia.

Exclusion Criteria:

- Severe psychological or physical illness.
- Inability to read and follow English instructions.
- High level of depressive symptoms.
- Unwillingness to participate in all aspects of the study.

Informed consent will be obtained, and participants will receive a stipend for their participation.

Methods: The effectiveness investigation of the Caring Light App (CLA) will be implemented with a pre-post randomized trial of 3 months. As it takes 3 months to complete the entire program, post testing will happen about 3 months after pre-testing. The trial will have two levels: the CLA treatment package; and a control condition comprised of existing educational programs, information for caregivers, and other resources. Outcome measures of both groups will be recorded at baseline and after 3 months.

- CLA Condition (75 subjects): Participants will receive the Caring Light mobile app containing the coping skills training.
- Control Condition (75 subjects): Participants will receive a traditional educational/resources program, containing a workbook and online resources.

Procedures: Participants will receive and complete informed consent. After initial assessment, subjects will be randomized to either CLA or the control condition, instructions will be distributed. After 3 months, all subjects will be interviewed for the post-intervention assessment.

Statistical Analysis Plan

Main study hypothesis: “CLA will alleviate depression (measured by CES-D), decrease stress (measured by PSS), and contribute to lower burden of care (RMBPC).

Main Outcome Measures:

- Depression: level of Depressive Symptoms: their presence and strength will be assessed using the Center for Epidemiological Studies Depression scale (CES-D); This is a 20-item measure that asks about the frequency of depressive symptoms (affective, psychological, and somatic) within the past week.
- Overall Perceived Psychological Stress: the 10-item Perceived Stress Scale (PSS) measures overall appraisals of stress in the past month.
- Burden of care: level of bother or stress due to disruptive behaviors: we will apply the Revised Memory and Behavior Problems Checklist (RMBPC), with 24 items describing possible troublesome behaviors of care receiver and effect (bother and stress) on caregiver.

Analysis: Our hypotheses will be tested by analyzing the change scores (subtracting the baseline scores from the value obtained at 3 months) for the outcome measures (CES-D, PSS, and RMBPC), and comparing the results of CLA with the control condition in order to determine the efficacy of the intervention. We will determine if subjects in CLA had a significant decrease in level of depression, reduced stress, and decreased burden, when compared to the control group. We'll use univariate ANOVA (analysis of variance) to determine the level of significance for these measures.

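### Eligibility lets two caregivers of the same person with dementia enroll and be randomized to opposite arms, so some controls may be exposed to CLA; the likely effect is small and one screening question prevents it

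*Combined protocol and SAP*

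**What the plan says.** The Research Participants section sets the sample as individuals: "150 dementia family caregivers (planned enrollment) will be recruited". The criteria that bear on the care relationship are "Care for an individual with Alzheimer's Disease or other dementia" and "Spend at least 8 hours/week caring for a person with dementia". The other two inclusion criteria concern device and Internet access and adult age. The four exclusions concern severe illness, ability to use English instructions, a high level of depressive symptoms, and "Unwillingness to participate in all aspects of the study". None mentions a relative already in the trial, a primary caregiver, or a shared care receiver.

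Under Procedures, "subjects will be randomized to either CLA or the control condition" after the initial assessment. Methods plans 75 per arm. No family or household unit is described.

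The three outcomes are the CES-D, the PSS and the RMBPC, the last "with 24 items describing possible troublesome behaviors of care receiver and effect (bother and stress) on caregiver". The Analysis paragraph compares change scores between arms by univariate ANOVA, with no term for a shared care receiver.

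**The concern.** A spouse and an adult child, or two siblings, can each give 8 hours of care a week to the same person and meet every listed criterion. Each would be randomized separately. If they fall in opposite arms, the control relative may be exposed to CLA in two ways.

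- **Directly.** The Project Summary describes self-paced training that includes advice on handling difficult behavior, along with stress-reducing exercises. Relatives who share care can pass such material on, and nothing in the documents asks participants not to.
- **Indirectly.** If the CLA relative manages the patient's behavior differently, the control relative may meet fewer or milder problems without ever seeing the app. The RMBPC is the outcome most open to this route.

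At stake is some loss of contrast between the arms. The documents describe no data item that identifies a shared care receiver, so as described the trial could not count such pairs or rule them out when interpreting a null result.

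**Working it through.** **Inputs from the documents.** 150 caregivers, 75 per arm (Research Participants; Methods). 75 + 75 = 150, so the stated total reproduces. The plan gives no alpha, power, effect size or SD, so there is no power statement to reproduce.

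**Assumed input.** The share of participants who enroll as pairs is not in the documents. A range is shown.

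**Step 1: chance that a pair is split.** With one member placed, 75 of the remaining 149 places are in the other arm: 75/149 = 0.503.

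**Step 2: expected split pairs.** (People in pairs / 2) × 0.503. Each split pair contributes one control, so dividing by 75 gives the share of controls affected.

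| Share in pairs | People | Pairs | Expected split | Share of 75 controls |
|---|---|---|---|---|
| 5% | 7.5 | 3.75 | 1.9 | 2.5% |
| 10% | 15 | 7.5 | 3.8 | 5.0% |
| 20% | 30 | 15 | 7.6 | 10.1% |

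If every affected control received the whole CLA effect, the between-arm difference would shrink by the last column. Partial carry-over shrinks it less.

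**Step 3: illustration in power.** Assume two-sided alpha 0.05 and 80% power without contamination; neither is in the documents. The detectable standardized difference with 75 per arm is √(2/75) × (1.960 + 0.842) = 0.457. With exposed share f and carry-over c, the diluted effect is 0.457 × (1 − f × c), and power is Φ(diluted effect / 0.1633 − 1.960), where 0.1633 = √(2/75). Pairs are rounded to whole numbers here, so f differs slightly from the table above.

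| Share in pairs | Pairs | f | Power, c = 50% | Power, c = 100% | Per arm to restore 80% |
|---|---|---|---|---|---|
| 5% | 4 | 2.7% | 78.9% | 77.8% | 78 to 80 |
| 10% | 8 | 5.4% | 77.8% | 75.5% | 80 to 84 |
| 20% | 15 | 10.1% | 75.8% | 71.2% | 84 to 93 |
| 30% | 22 | 14.8% | 73.7% | 66.6% | 88 to 104 |

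Up to 10% in pairs, the loss is at most 4.5 points (80 − 75.5). It becomes material at 20% to 30%.

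**Step 4: does ignoring pairs disturb the ANOVA?** The type I error was simulated with 20,000 runs per setting, 10% or 30% of participants in pairs, and an assumed within-pair correlation of 0.3 or 0.6. Under individual randomization, as planned, it was 0.049 to 0.053. It reached 0.054 to 0.068 only when all pairs were forced into the same arm, and fell to 0.032 to 0.045 when all were forced apart. Under individual randomization the two kinds of pair occur about equally often and roughly cancel.

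**The case against.** The strongest reply is that the harm is hypothetical. Nothing in the documents shows that two relatives of one patient will enroll: no recruitment source or family referral is described, and the Project Summary puts the caregiver population at more than 15 million against a need for 150. Each participant uses their own device and the program takes 3 months, so having a relative with the app is far from receiving its full effect. This stands. It makes the figures upper limits under assumed shares, but it does not close the gap in eligibility.

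Three stronger readings are tempting, and the documents support none of them.

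- **A reader might infer that non-independent pairs invalidate the ANOVA.** Under the individual randomization that the plan describes, the simulated error rate stays near 5%.
- **A reader might infer that the RMBPC would record the same rating twice.** The behaviors would be those of one patient, but the Main Outcome Measures define burden as each caregiver's own reaction to them. Two relatives' scores may correlate without being duplicates. The CES-D and PSS concern the caregiver alone.
- **A reader might infer that the bias can run only toward no effect.** Dilution is the more probable direction. But the outcomes are self-reported and no blinding is described, so a control who sees a relative receive the app might also report worse scores from disappointment. The documents do not settle this.

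**Conclusion.** The gap is real and the point holds as a low-severity one. The plan permits co-caregivers of one patient to be split between arms, and has no means of preventing, counting or handling it. For assumed pairing of 5% to 20%, between 2.5% and 10% of controls would have a co-caregiver in the CLA arm, and the proportional dilution could be at most that large. Whether any dilution occurs depends on two things the documents do not give: how many pairs enroll, and how much of the intervention reaches the control member. A split pair makes exposure possible, not certain. The case for acting rests on the low cost of prevention, not on a demonstrated large bias.

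**What to change.** Add to the inclusion criteria: *Only one caregiver per person with dementia may be enrolled.* Check it with one screening question asking whether anyone else caring for the same person is taking part. The limit should apply per person with dementia; nothing in the documents justifies a wider bar on caregivers of different patients who share a household.

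If pairs are already enrolled, flag them and repeat the three comparisons (CES-D, PSS, RMBPC) as a sensitivity analysis, excluding split pairs, or at least their control members, and keeping one member of each same-arm pair by a rule fixed before outcomes are examined. Simply keeping whoever enrolled first is not enough for split pairs: in about half of them that person would be the control, who stays in the analysis still exposed. At 10% pairing that is about 3.8 / 2 = 1.9 controls. The sensitivity analysis shows how far the result depends on these pairs; it does not reverse exposure that has occurred.

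The cost is one eligibility line, one screening question, and a few willing second relatives turned away.

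### Does the lack of an assessment window around the 3-month post-test leave the change score undefined?

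*Combined protocol and SAP*

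**What the plan says.** The combined protocol and SAP speaks of post-test timing in five places.

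- Methods gives the reason for the interval and its starting point: "As it takes 3 months to complete the entire program, post testing will happen about 3 months after pre-testing".
- Methods, a little further on: "Outcome measures of both groups will be recorded at baseline and after 3 months".
- Overview, step 5, listed after the step that sends out materials: "We will collect post-treatment data after 3 months".
- Procedures, after randomisation and distribution of instructions: "After 3 months, all subjects will be interviewed for the post-intervention assessment".
- Statistical Analysis Plan, Analysis, which defines the change score as "subtracting the baseline scores from the value obtained at 3 months".

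None of these gives a tolerance in days, a latest acceptable date, or a rule for an interview held off schedule. The only tolerance is the word about, in Methods.

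**The concern.** Two things look loose.

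The first is the origin. Methods justifies the interval by the length of the program but counts it from the pre-test. Access cannot begin at the pre-test, because Procedures says "After initial assessment, subjects will be randomized to either CLA or the control condition, instructions will be distributed". Procedures and Overview step 5 then give the interval straight after a dispatch step, so a reader could count from dispatch instead. If the count runs from the pre-test and delivery is slow, some participants would be assessed before a full 3 months of access.

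The second is the missing window. All three outcomes (CES-D, PSS and RMBPC) are analysed as change scores to 3 months. If it is not settled whether an interview at, say, 2 or 5 months counts, an analyst could decide after seeing the data, and that would be an unplanned choice between two analyses. The recall periods are short (one week for CES-D, one month for PSS), so interviews that ran later in one arm than in the other would also cover different periods of the caregivers' lives.

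**Working it through.** **Origin, by comparing the statements.**

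| Place | Interval | Starting point stated |
|---|---|---|
| Methods, first statement | about 3 months | pre-testing |
| Methods, second statement | 3 months | baseline, on a literal reading |
| Overview, step 5 | 3 months | none |
| Procedures | 3 months | none |
| SAP, Analysis | 3 months | none |

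One origin is named, a second statement agrees with it, and the other three are silent. Silence in a summary does not contradict the sentence that gives the detail.

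**Which value is analysed.** The plan has one baseline and one post-intervention interview per participant, so there is no choice among several follow-up values. Procedures has all participants interviewed, and the analysis paragraph contains no exclusion by date. Followed as written, each post-test obtained is the 3-month value.

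**Size of the risk if someone departed from that reading.** The documents give 75 participants per arm. They give no share of off-schedule interviews, significance level, power or effect size. I assume a two-sided 5% test, complete follow-up, a share f of interviews in each arm falling outside a window set later, and exclusion unrelated to outcome.

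The test statistics from all interviews and from the in-window subset have correlation √(1 − f). The chance of a false positive from at least one of them is P(|Z₁| > 1.96 or |Z₂| > 1.96) under the bivariate normal distribution. The detectable difference is for a two-sample t-test with 80% power; the number left per arm is 75 × (1 − f), rounded.

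| f | Correlation | At least one p < 0.05, no true effect | Left per arm | Detectable difference |
|---|---|---|---|---|
| 0 | 1 | 5.0% | 75 | 0.46 SD |
| 5% | 0.975 | 6.0% | 71 | 0.47 SD |
| 10% | 0.949 | 6.5% | 68 | 0.48 SD |
| 20% | 0.894 | 7.1% | 60 | 0.52 SD |

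The excess over 5% is 1.0 to 2.1 percentage points per outcome, and it arises only if whichever analysis looks better may be reported.

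**Exposure, as illustration only.** Take 3 months as 91 days and suppose delivery takes 3, 7 or 14 days. The shortfall in access is 3/91 = 3%, 7/91 = 8% or 14/91 = 15%, and nil with same-day delivery. If the effect were strictly proportional to elapsed time and everyone were tested at exactly 91 days, power of 80% at 0.46 SD would become 77%, 73% or 66%. The plan supports none of these conditions: it allows an approximate interval, the program is self-paced, and 0.46 SD is solved backwards from 75 per arm rather than planned.

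**The case for a change.** The best case for acting is that the remedy is nearly free: one sentence on origin, one on the window, one on handling, and a recorded dispatch date. Against that small cost, a plan silent on off-schedule interviews leaves room for a later decision to drop them. The tension in Methods is also real: a 3-month program counted from the pre-test fits exactly only if delivery is immediate, and no limit on delivery time is given.

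Part of this stands. There is no window and no off-schedule rule, and the origin is stated once rather than repeated. What does not stand is the step from silence to permission: nothing in the text provides for leaving out interviews by date, and the plain reading uses them all. Nor would changing the origin clearly improve the trial. Counting from the pre-test keeps the baseline-to-post interval equal across arms; counting from dispatch secures full program time. Either is defensible. A dispatch date would show time of access rather than use, for a self-paced program in a plan with no exposure analysis. Lateness that differed between arms would matter more, but nothing in the documents points to it, and both arms share one schedule.

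**Conclusion.** No change to the plan follows. The gap is missing detail that an analyst fills in the obvious way: count from the pre-test, as Methods says, and analyse every post-test whatever its date. Done so, the comparison of change scores is a valid randomised comparison, and no result or conclusion depends on a window being written down.

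The false-positive figures of 6.0% to 7.1% describe a departure from the plan, not the plan itself. They rest on an assumed off-schedule share of 5% to 20%, a window set after the fact, and selective reporting. The exposure figures rest on an assumed delivery lag and an assumed proportional effect, and carry no weight in this conclusion.

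The conclusion rests on two readings: that the single post-test is the 3-month value even when it falls somewhat early or late, and that both arms are interviewed on the same schedule. The text supports both. If the investigators ever do apply a window, it belongs in a sensitivity analysis beside the analysis of all post-tests.

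### Change-score ANOVA fixes the baseline coefficient at 1; adjusting for the baseline score by ANCOVA would be more precise at almost no cost

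*Combined protocol and SAP*

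**What the plan says.** The Analysis paragraph of the Statistical Analysis Plan is the whole analysis plan for the three main outcomes, CES-D, PSS and RMBPC. It defines the analysed variable: "Our hypotheses will be tested by analyzing the change scores (subtracting the baseline scores from the value obtained at 3 months"). The purpose is "comparing the results of CLA with the control condition in order to determine the efficacy of the intervention", and the test is "univariate ANOVA (analysis of variance) to determine the level of significance for these measures". Neither the protocol nor the SAP mentions a covariate, an ANCOVA, another baseline-adjusted model or a sensitivity analysis.

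The data for an adjusted analysis will exist. Under Methods: "Outcome measures of both groups will be recorded at baseline and after 3 months". Under Procedures: "After initial assessment, subjects will be randomized to either CLA or the control condition". Allocation is 75 to each arm, 150 in all. No stratification of the randomization on baseline score is described, so the design does not control baseline imbalance either.

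**The concern.** A change score does use the baseline, but with a coefficient fixed at 1. The coefficient that minimises the variance is the slope of the 3-month score on the baseline score. With similar spread at the two visits, that slope equals the pre-post correlation. These are self-report scales measured about three months apart, and two of them ask only about the past week or month, so a correlation close to 1 is implausible. Subtracting the full baseline then adds noise and leaves the change score negatively correlated with baseline.

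Two things are at stake. First, all three main comparisons are likely to lose power, and the documents contain no power calculation that would show there is power to spare. Second, if one arm starts worse by chance, regression to the mean will make that arm appear to improve more, and the planned test does not remove this.

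**Working it through.** **Inputs from the documents.** 75 per arm; one baseline and one 3-month value per outcome; ANOVA on the difference, with no covariate.

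**Assumptions, because the documents give no figures.** Two-sided 5% level; no dropout; outcome SD set to 1 at both visits; pre-post correlation r shown over a range. The planned enrollment of 150 comes with no level, power, effect size or SD, so there is no sample-size calculation to reproduce.

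**Precision.** Per-person variance of the analysed quantity:

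- change score: 1 + 1 − 2r = 2(1 − r)
- ANCOVA residual: 1 − r² = (1 − r)(1 + r)
- ratio, change to ANCOVA: 2/(1 + r), which exceeds 1 for every r below 1

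The ANCOVA-equivalent sample is 150 ÷ ratio. For power, a two-sample t-test with 75 per arm has 80% power at 0.460 SD of the analysed variable. Multiplying the corresponding noncentrality by √ratio gives the ANCOVA power (noncentral t).

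| r | ratio | 150 on change is worth | ANCOVA power where change gives 80% | power for a 0.4 SD effect, change → ANCOVA |
|---|---|---|---|---|
| 0.4 | 2/1.4 = 1.43 | 105 | 92% | 60% → 76% |
| 0.6 | 2/1.6 = 1.25 | 120 | 88% | 78% → 86% |
| 0.8 | 2/1.8 = 1.11 | 135 | 84% | 97% → 98% |

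The 0.4 SD effect is illustrative. A simulation of 20,000 trials with 75 per arm and that effect, which includes the cost of estimating the slope, gave 68.2% against 80.1% power at r = 0.5, and 87.9% against 92.3% at r = 0.7.

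When r is below 0.5, 2(1 − r) is greater than 1. The change score is then less precise than the 3-month score with baseline ignored.

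**Chance imbalance.** The standard error of the baseline difference between arms is √(2/75) = 0.163 SD. Given an observed imbalance, the change-score estimate is off by (r − 1) × imbalance, opposite in sign to the imbalance. A one-standard-error imbalance at r = 0.6 gives −0.4 × 0.163 = −0.065 SD. In the simulation, the slope of the estimate on the imbalance was −0.50 (r = 0.5) and −0.31 (r = 0.7) for change scores, and about 0 for ANCOVA.

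**CES-D.** The Exclusion Criteria remove caregivers with a high level of depressive symptoms but give no threshold or screening scale. Suppose this cuts off the top 10% to 30% of a normal baseline CES-D distribution. Selection on baseline leaves the slope and residual variance unchanged and reduces the baseline variance to a fraction v = 1 − cλ − λ², where c is the cut-point and λ = φ(c)/Φ(c). The ratio becomes 1 + v(1 − r)/(1 + r), with r the correlation before truncation.

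- Top 10% removed: v = 0.71; at r = 0.5, 1 + 0.71 × 0.5/1.5 = 1.24.
- Top 30% removed: v = 0.49; at r = 0.7, 1 + 0.49 × 0.3/1.7 = 1.09.

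Over these ranges the ratio is 1.09 to 1.24, and 80% power on change becomes about 83% to 88%.

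**The case against.** The strongest reply is that nothing here is invalid. Under randomization the change-score comparison holds its type I error and is unbiased on average: in the simulation both estimators averaged about −0.40 for a true effect of −0.40. The imbalance error is conditional on the imbalance that happens to occur. All of that stands, and it makes this a matter of efficiency rather than of a false claim.

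Second, the loss depends on the slope, not on r alone. With s the ratio of the 3-month SD to the baseline SD, the slope is rs and the variance ratio is 1 + (1 − rs)²/[s²(1 − r²)]. At r = 0.7 and s = 1.2 this is 1.035; at r = 0.8 and s = 1.25 the slope is exactly 1 and the ratio is 1.00. This also stands: a larger spread at 3 months can shrink the gain or remove it. But the squared term cannot be negative, so in expectation ANCOVA gives up nothing beyond the small cost of estimating one slope.

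Third, the size is not fixed by the documents. For a 0.4 SD effect, a normal approximation puts the loss at about 18 percentage points at r = 0.3 and about 1 point at r = 0.8. Hence the ranges above.

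Fourth, the protocol's Overview lists randomization before collection of baseline data, whereas Procedures places it after the initial assessment. A baseline taken after allocation could be influenced by it. The order should be confirmed, but the change score relies on the same baseline, so this does not favour the planned method.

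**Conclusion.** The concern holds. The planned test is valid but less efficient than ANCOVA whenever the slope on baseline differs from 1. With equal variances and r between 0.4 and 0.8, the variance penalty is 11% to 43%, equivalent to setting aside 15 to 45 of the 150 participants. For CES-D under the assumed truncation the penalty is 9% to 24%. Chance imbalance is over-corrected by a modest amount. The direction is secure under equal variances; the magnitude rests on correlations and SDs that the documents do not give. The plan should be changed, but the trial's conclusions would not be invalid if it were not.

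**What to change.** Replace the change-score ANOVA with an ANCOVA for each of CES-D, PSS and RMBPC: the 3-month score as response, arm as factor, and the baseline value of the same scale as covariate. Using change as the response with the same covariate gives the identical treatment effect. Report the adjusted mean difference with its 95% CI; mean changes by arm can stay as description.

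Fix the model before outcome data are examined by arm. If they have already been examined, present the adjusted result as post hoc beside the planned one. At the same time, reconcile the Overview and Procedures on whether baseline assessment precedes randomization.

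The cost is one sentence of SAP wording and one degree of freedom per model, with no new data, participants or visits.
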